The Fitbit mobile app and device require the creation of individual accounts with Fitbit for all study participants within the Fitbit app on a smart phone or tablet. Participants will be asked to use an email address of their choosing and accept Terms and Conditions for use of the Fitbit app. The data collected from the Fitbit devices will NOT be integrated with the medical record of the patient or used for clinical decision making. FitBit data will be collected through syncing with the FitBit app on a smart phone or tablet at least weekly by the participant. The Fitabase platform will be used to remotely collect real-time physical activity and sleep data from study participants' Fitbit accounts, and also to send personalized text messages to participants' cell phones. Participants will be asked to accept the Fitabase Terms and Conditions for linking with the Fitbit App. Fitabase is a secure password-protected web-based platform hosted in a HIPAA-compliant server. Fitabase comprises user-friendly visualization and data exportation tools that allow key research personnel to view participants' Fitbit data in the form of graphs every time participants sync their wearable tracker with the Fitbit mobile app. Study participants will not have access to Fitabase; they will only interact with the Fitbit mobile app and activity tracker. The text messaging feature is integrated with Fitabase and utilizes Twilio's application programming interface to send messages via the SMS protocol. Participants will be consented to utilize their smart phone devices for syncing with the Fitbit app and to receive text messages from the platform to serve as reminders to sync devices and to utilize the online resources for those in the intervention phase. The only identifier shared with the Fitabase platform and Twilio, Inc. is the telephone number for the smart phone device the participant consents to utilize. Participants will be asked to use and email address of their choosing to create an account within the Fitbit App.

All risks associated with the intervention will be minimized by allowing participants to discontinue the intervention at their discretion and the study team will regularly assess adverse effects of the intervention.

If participants suffer any unforeseen harms including psychological, emotional, physical, they will be encouraged to contact the PI or the IRB. Contact information will be provided in the consent forms including telephone, mail, and email.

a. Sharing of Results with Subjects

Data from this clinical trial will not be shared directly with participants. The results of the clinical trial and de-identified data will be made in accordance with NIH regulations and clinicaltrials.gov.

b. Data and Specimen Banking

No specimens will be stored. Study records will be retained for the longest regulatory retention period. After that time, records will be destroyed in a confidential manner.

8. Data Analysis

See Table 1 for outline of data analysis planned for study outcomes. As this is a pilot intervention trial, the focus will be on feasibility and acceptability of the pragmatic intervention trial. We will also explore effectiveness outcomes, but recognized we will be underpowered for a definitive effectiveness trial within this heterogeneous population selected to be representative of the population of interest. We will use our pilot trial to inform a future larger trial that will include longitudinal real world health outcomes relevant to the pediatric TBI population if supported by our preliminary results.

Prior to evaluating outcomes, we will perform a thorough descriptive analysis of participant baseline characteristics (age, race, ethnicity, gender, pre-injury comorbidities, TBI characteristics including severity, location, and type). We will examine patterns of missingness in our outcomes collected at 1-month, differences in participant and non-participant characteristics, and differences in participants who completed versus dropped out of the study to ascertain potential bias. Additionally, we will describe and compare the distribution of patient and clinical characteristics, including age and TBI severity, across treatment groups to ensure our randomization protocol was successful. Comparisons between groups will be made using chi-square tests for categorical variables. Depending on characteristics of the data, t-tests and Mann-Whitney U tests will be used to compare continuous variables between groups. We plan to perform both intention to treat and per protocol analyses.

Quantitative feasibility outcomes will be presented as a percentage of patients, the denominators of which are listed in Table 1. Comparisons between groups will be made with chi-square tests.

Quantitative acceptability outcomes for adverse events will be dichotomized to yes/no and evaluated as a total number for each patient summarized using percent and median with interquartile range (IQR), respectively. Acceptability outcomes for satisfaction will be measured using Likert scales for which we will present results as medians and IQR. Chi-square tests will be used to compare dichotomized outcomes between treatment groups, and Mann-Whitney U tests will be used to compare total number of events. Effectiveness outcomes will be summarized using means and standard deviations, except for daytime sleep episodes which will be summarized as a median and IQR; these outcomes will be summarized for the overall study population and by treatment group. We will primarily examine the effectiveness of our intervention using linear regression to assess differences in the total SDSC score across treatment groups at 1-month. Linear regression will allow us to assess differences in effectiveness outcomes while controlling for covariates that may confound this relationship; covariates of particular interest will include age and TBI characteristics. Covariates identified in our initial descriptive analysis as significantly different between treatment groups, and covariates significantly associated with SDSC total score in bivariate analyses will also be explored with multiple linear regression.

Secondary effectiveness outcomes that specifically evaluate sleep phenotypes (measured by questionnaire and actigraphy) will be similarly evaluated with linear regression, except daytime sleep episodes which will be modeled using a count model, such as Poisson or negative binomial regression. For these secondary effectiveness outcomes, our focus is the magnitude of the association rather than statistical significance, as multiple comparisons will be made. Our primary goal with this secondary analysis will be to determine if the intervention appears effective for particular phenotypes that could be targeted in future studies. Results of these secondary analyses will be used as estimates for effect sizes in future intervention study design.

Qualitative analysis of survey responses for feasibility and acceptability outcomes (Table 1) will be analyzed with thematic network analysis. Transcription of survey responses will be coded using a hybrid approach: 1)based on the pre-specified survey questions administered (deductive approach); 2)creating new codes as needed based on participant responses to open ended questions (inductive approach). Coded transcripts will be used to construct thematic networks identifying global and organizing themes reported among responses. Exploration and description of thematic networks will be used to identify patterns within data for interpretation.

9. Privacy, Confidentiality, and Data Security

Data and protected health information will be safeguarded in multiple ways. All data will be stored on and OHSU secure drive or in the OHSU secure REDCap database, which is encrypted, and password protected. Access to REDCap will be controlled by the PI and is stored on an OHSU encrypted and password protected server. All study forms will include only a study ID number. All study data will be inputted into REDCap by members of the study team trained in Human Subjects Research and Responsible Conduct of Research as well as study procedures. The PI will maintain the REDCap database and provide access only to study team members. All exports of data from REDCap will be coded.

10. Provisions to Monitor the Data to Ensure the Safety of Subjects

Adverse events related to the intervention trial will be assessed at hospital discharge, and at 30-days via clinic visit, survey, and medical record review. All adverse events will be recorded and reported as required.

A Data and Safety Monitoring Plan (DSMP) including the provision of an institutional Data Safety Monitoring Board (DSMB) will be submitted as a separate documents for approval to the IRB.

As this trial is a pilot investigation, we do not have prespecified stoppage criteria. Trial progress and safety will be closely monitored by the PI and DSMB. The PI will review Serious Adverse Events (SAEs) as they occur and the DSMB will review SAEs at each meeting and on an as-needed basis. The DSMB will review trial progress and safety. The DSMB recommendations may include study continuation without modification, study termination, study continuation with protocol modification, or temporary suspension of enrollment until further evaluation is completed. The DSMB will review each death occurrence. Cumulative SAEs for each study arm will be provided to the DSMB and reports will be submitted to the study team, IRB, program staff at the National Institutes of Health, and the Food and Drug Administration as required. If the PI is notified of any SAE that is thought possibly related to the study, the participant will be immediately withdrawn.

11. Risks and Benefits

a. Risks to Subjects

Intervention risks will be considered more than minimal risk, but with potential to directly benefit the participant. Melatonin has demonstrated a good safety profile in multiple studies involving children and is available as a dietary supplement over the counter. A concern regarding use of over the counter melatonin is the variability in content and contaminants within supplements noted from lack of FDA oversight of dietary supplements.[87] We have minimized this risk by working with a manufacture that has provided Chemistry and Manufacturing Control data reviewed and approved for use by the FDA IND application. No serious adverse events have been reported with melatonin use in short or long-term studies as noted above. Studies using melatonin have reported symptoms including: dermatologic (itchy skin, rash), gastrointestinal (stomach upset, appetite changes, emesis), neurologic (drowsiness, blurred vision, vivid dreams), and bodily pain. Placebo studies report similar symptoms. Melatonin may affect levels of medications metabolized in the liver (particularly through CYP1A2 and CYP450 enzymes) or that are conjugated in the liver to sulfuric or glucuronic acid. There are unclear effects of melatonin on auto-

immune disorders and immune function. Melatonin is considered a dietary supplement, and as such, not regulated by the Food and Drug Administration. All risks will be communicated to the participant and included in the written consent provided to participants.

No serious adverse events were reported in recent meta-analyses of studies using melatonin conducted in children with neurodevelopmental disorders, including epilepsy, or in a recent adult trial comparing melatonin and placebo, but melatonin appeared to effectively improve sleep. No serious adverse events were reported in a recent randomized trial in pediatric concussion using doses up to 10mg (double this trial's maximum dosing).[76] The potential benefit of improved sleep after TBI in our study compared to the risk associated with melatonin is likely as favorable to standard care given >50% have disturbed sleep after discharge without treatment and SWD are associated with worse cognitive functions and quality of life in pediatric TBI patients.

Given the ubiquitous use of melatonin in pediatric clinical care and research studies in a variety of pediatric populations with medical, developmental, and psychiatric disorders, no patients will be excluded for underlying medical conditions or concomitant medication use, outside of exclusion criteria above. Patients will be excluded from the trial if the clinical care Attending Physician deems the patient unable to tolerate enteral medications or otherwise has safety concerns regarding use of melatonin.

There will be no requirement for use of contraception in female participants of child-bearing age given no known adverse effects of melatonin in pregnancy and short duration of the intervention. Pregnant patients will be excluded from the trial or withdrawn immediately from the trial if become pregnant.

The educational intervention proposed in this study is of minimal risk given it is a handout with resources to promote healthy sleep. As part of our acceptability outcomes, we will evaluate utilization and usefulness of this portion of the intervention.

Data collection, questionnaire and survey risks include loss of confidentiality. Participants will provide questionnaire and survey data via paper forms, electronic survey through REDCap, or telephone interview at 30-day time points. Paper forms will only contain the subject study ID without other identifiable information to minimize risk of loss of privacy and confidentiality. Paper forms will be entered by a Research Assistant into REDCap. Access to identifiable information will be limited to study personnel and not shared with anyone outside the research group. Every effort will be made to minimize risk of loss of confidentiality. All study related paper forms will be destroyed after completion of the study.

Actigraphy risks include loss of confidentiality and minor physical discomfort. Participants will wear actigraphy devices for a period of one month that pose no more than minimal risk to subjects. Actigraphy devices will be distributed to participants during clinical visits or via mail. System generated text messages are sent weekly to remind participants to sync with the smartphone app to collect actigraphy data. Participants will be consented for use of text messaging and can opt out at any time by contacting the research team.

Study computers are password protected and encrypted within the OHSU network firewall and access will only be granted to study team members to minimize risk of loss of confidentiality. Actigraphy devices are non-invasive and can be freely removed by participants, but there is a small risk of discomfort related to the device. Participants will be allowed to withdraw from this portion of the study if desired.

b. Potential Benefits to Subjects

Participants may directly benefit from the intervention given the high prevalence of sleep disturbances after TBI, and literature supporting melatonin and sleep educational interventions in pediatric populations with SWD targeting the most prevalent sleep problems seen after pediatric TBI. While the placebo arm may not benefit directly from intervention, the increased focus on sleep through

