We expect to enroll between 30-50 patients based on eligibility over 2.5 years of recruitment. This estimate is based on the most recent hospital admissions data since the start of the COVID-19 pandemic estimating approximately 100 patients will qualify for the study over 2.5 years. Participants will be randomized 1:1 to receive the intervention. Recruitment and retention will be assessed during the trial as outcomes.

b. Inclusion and Exclusion Criteria

Children \geq 6 years and <19 years of age admitted with TBI (defined as injury to the head from external forces with severity mild, moderate, or severe classified by Glasgow Coma Scale) will be included.

Children under the age of 6 years will be excluded due to increased variability in baseline sleep patterns, daytime napping, and lack of standardized tools identifying sleep outcomes between children younger and older than 6 years. Patients over age 18 years will be excluded as they are primarily treated in adult care units and the study focus is pediatric. Patients unable to tolerate enteral medications within 72 hours of hospital admission, as defined by the clinical care Attending Physician, will be excluded from the study. Patients undergoing dialysis, requiring extracorporeal life support, or with significant liver dysfunction (defined as aspartate aminotransferase (AST) or alanine aminotransferase (ALT) more than 2 times the upper limit of normal for age) will be excluded. Patients about whom the Attending Physician has any safety

concerns regarding use of melatonin as per clinical judgement will be excluded from the study. Patients with abusive trauma will be excluded. Suspected or known prisoners are excluded. Pregnant patients are excluded. There will be no requirement for contraception during the trial in female patients of child-bearing age. Patients must have a parent or guardian with whom they reside in order to participate in the study given the parent-reported measures used for outcomes.

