There is inherent heterogeneity in the pediatric TBI population, and this study is designed to be *inclusive of the representative clinical population*, including those with pre-existing conditions. Given the ubiquitous use of melatonin in pediatric clinical care and research studies in a variety of pediatric populations with medical, developmental, and psychiatric disorders, no patients will be excluded for underlying medical conditions or concomitant medication use outside of the above exclusion criteria unless clinical judgement by the Attending Physician on the clinical care team would preclude use of melatonin for safety concerns.

Potential participants will be screened on arrival through the OHSU Emergency Department (all traumas, suspected traumas, and trauma referrals from other institutions are evaluated by the Trauma Surgery team in the Emergency Department per OHSU policy prior to admission). Medical records will be reviewed by the study team to determine eligibility; a waiver of consent under "Activities Preparatory to Research" for participant eligibility determination by research coordinators will be obtained. Research coordinators with the Trauma Research Group are present in the Emergency Department and are available to screen all TBI admissions for inclusion into active research studies 24hours/day. Screening information regarding inclusion/exclusion criteria will be retained for further analysis of recruitment outcomes.

c. Vulnerable Populations

The aims of this study are entirely focused on children ≥ 6 years to <19 years old. Inclusion of children is appropriate given the proposal focus on sleep outcomes in pediatric traumatic brain injury. Traumatic brain injury is a significant problem for children, including the leading cause of death and disability over 1 year of age. [name] is a Pediatric Critical Care physician with significant expertise in caring for children of all ages with critical illnesses, including traumatic brain injury, during the acute hospitalization. [name] also has unique expertise in the longitudinal care of these children after discharge, directing the Pediatric Critical Care and Neurotrauma Recovery Program. Age will be evaluated as a covariate in the analysis of both aims. Pregnant patients and prisoners are excluded.

d. Setting

Patients will be recruited from OHSU and Doernbecher Children's Hospital

e. Recruitment Methods

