Randomization: Patients will be randomized 1:1 to intervention and control arms using a covariate adaptive design through the randomize.net website. Given heterogeneity in age and TBI severity, we aim to balance these patient characteristics across the arms with a relatively small sample size. A covariate-adaptive design will achieve better balance than one based on block stratification, as such a scheme will increase a subject’s probability of being assigned to the arm that improves overall balance in age and TBI severity (Glasgow Coma Scale Score groups: mild 13-15, moderate 9-12, severe ≤ 8). Initially, we will assign patients 1:1 to each arm by simple randomization, until six patients have been enrolled in each arm; this will allow us to collect sufficient information on covariates and determine the distribution of age and TBI severity in each arm. Once this criterion has been met, the Pocock-Simon minimization algorithm will be implemented and subsequent patients will be randomized with a probability of 0.85 to the arm that lowers overall imbalance in age and TBI severity. All patients will be randomized within 72 hours of hospital admission.

Intervention: All patients will receive standard clinical care for TBI regardless of study arm. Patients randomized to the intervention will receive a bundled sleep intervention consisting of melatonin and sleep education via a handout provided in discharge paperwork. Melatonin doses of 3mg and 5mg will be administered as part of the intervention arm in standard doses based on patient weight to target approximately 0.1mg/kg and not to exceed 0.2mg/kg. Melatonin will be administered on the first night following consent, 1 hour prior to habitual bedtime, and continued nightly for 30-days. Each participant will start the melatonin or placebo intervention within 96 hours of hospital admission, varying with time of admission and consent. Patients randomized to receive the intervention will be given a written sleep education handout developed with age-based recommendations from the American Academy of Sleep Medicine and access to web-based sleep educational resources developed from similar materials used in the care of pediatric brain injury patients within the outpatient setting.

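### Age is promised as a covariate for both aims, but the adverse-event, adherence and satisfaction arm tests take none, and under minimisation they can be conservative where age and GCS group predict the outcome

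*Combined protocol and SAP*

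**What the plan says.** Section 5c (Vulnerable Populations) says "Age will be evaluated as a covariate in the analysis of both aims". The aims are never numbered. Sections 2 and 4 make feasibility and acceptability the focus and add exploratory effectiveness, so those two are the natural reading.

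Section 5a plans 30–50 patients and says "Participants will be randomized 1:1 to receive the intervention". Section 6 (Randomization) sets the allocation in two phases: "Initially, we will assign patients 1:1 to each arm by simple randomization, until six patients have been enrolled in each arm"; after that, "subsequent patients will be randomized with a probability of 0.85 to the arm that lowers overall imbalance in age and TBI severity". Severity enters as three groups ("Glasgow Coma Scale Score groups: mild 13-15, moderate 9-12, severe ≤ 8"). No age bands are given.

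For feasibility outcomes Section 8 says "Comparisons between groups will be made with chi-square tests". For adverse events it uses chi-square on the yes/no form, and "Mann-Whitney U tests will be used to compare total number of events". Table 1 agrees: chi-square for adherence, chi-square and Mann-Whitney for adverse events, Mann-Whitney for satisfaction.

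Covariates enter only for effectiveness: "Linear regression will allow us to assess differences in effectiveness outcomes while controlling for covariates", with age and TBI characteristics singled out.

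**The concern.** There are two mismatches. In the text, Section 5c commits to age as a covariate in both aims, but no arm comparison named for the first aim can carry a covariate. In the design, age and GCS group are thought important enough to force balance on and to adjust for in the exploratory outcomes, but are left out of the one starred acceptability outcome.

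The design mismatch can matter statistically. Forced balance removes part of the chance difference between arms, while an unadjusted test still allows for it. If age and GCS group predict the outcome, the test rejects less often than its nominal level and loses power. For adverse events that error leans towards reporting no difference.

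**Working it through.** **Plan's own figures.** The plan states no significance level, power, adverse-event rate, or strength of link between age or GCS and these outcomes, so there is no such figure to reproduce. Two-sided 5% is assumed throughout.

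**Step 1: what forced balance does.** For N patients split equally, with outcome variance σ² and a share R² explained by age and GCS group:

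- variance assumed by an unadjusted test: (4/N)σ²
- true variance under perfect balance: (4/N)σ²(1 − R²)
- limiting size: 2Φ(−1.96/√(1 − R²))

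R² = 0 gives 5.0%. R² = 0.1 gives 2Φ(−1.96/0.949) = 2Φ(−2.066) = 3.9%. R² = 0.4 gives 2Φ(−1.96/0.775) = 2Φ(−2.530) = 1.1%. Real balance is imperfect: the coin is 0.85, and at least 2 × 6 = 12 patients (12/50 = 24% to 12/30 = 40%) are allocated before minimisation starts.

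**Step 2: simulation of the Section 6 allocation.** From the plan: simple randomisation to six per arm, then Pocock-Simon at 0.85 on age and three GCS groups; N = 30 to 50. Assumed: three age bands (30/35/35%); GCS mix 60/15/25%; no drop-out; yes/no risk about 40%; harm odds ratio 3.5; negative binomial event count with mean about 3 and harm ratio 1.8. Link strength is the odds ratio (OR) per level of age band and GCS group. The log count moves half as much, so OR 1.65 means a count ratio of √1.65 = 1.28 per level, and OR 2.7 means √2.7 = 1.64. The adjusted analyses are linear regressions (on ranks for counts, on 0/1 for yes/no) with arm, age-band score and GCS group. With 5,000 trials per cell, the simulation error is √(0.05 × 0.95/5000) = 0.3 points for size and at most √(0.25/5000) = 0.7 points for power.

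Event count, Mann-Whitney v adjusted ranks (%):

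| N | Link | Size | Power | Gain |
|---|---|---|---|---|
| 30 | none | 4.0 v 4.5 | 45.7 v 46.2 | +0.5 |
| 30 | age only, 1.65 | 4.4 v 5.2 | 43.7 v 45.2 | +1.5 |
| 30 | both, 1.65 | 4.1 v 5.4 | 40.2 v 44.9 | +4.7 |
| 30 | both, 2.7 | 2.8 v 5.5 | 28.3 v 42.7 | +14.4 |
| 50 | none | 4.8 v 4.9 | 69.2 v 69.5 | +0.3 |
| 50 | age only, 1.65 | 4.3 v 5.1 | 67.4 v 68.8 | +1.4 |
| 50 | both, 1.65 | 4.2 v 5.3 | 63.3 v 68.4 | +5.1 |
| 50 | both, 2.7 | 2.4 v 5.2 | 49.0 v 67.0 | +18.0 |

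Under simple randomisation with OR 2.7, Mann-Whitney size is 4.6–5.0%, so the shortfall at that strength comes from the minimisation.

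Yes/no outcome, chi-square v adjusted linear model (%):

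| N | Link | Size | Power | Gain |
|---|---|---|---|---|
| 30 | none | 4.8 v 5.1 | 37.0 v 37.1 | +0.1 |
| 30 | both, 1.65 | 4.6 v 5.3 | 31.0 v 33.5 | +2.5 |
| 30 | both, 2.7 | 3.1 v 5.2 | 23.1 v 30.2 | +7.1 |
| 50 | none | 5.6 v 4.6 | 63.0 v 58.0 | −5.0 |
| 50 | both, 1.65 | 5.1 v 5.0 | 56.2 v 54.6 | −1.6 |
| 50 | both, 2.7 | 3.5 v 4.5 | 43.1 v 46.6 | +3.5 |

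An adjusted logistic score test ran at 5.6–7.6%, so part of its apparent power gain is inflated size.

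**Step 3: a second parameterisation.** With a 0–19 symptom count and a 0.8-SD excess, Mann-Whitney size is 3.4–4.0% at R² = 0.1 and 1.6–2.5% at R² = 0.4, against 4.7–5.6% for adjusted ranks. At N = 40, power is 67% against 70% (R² = 0.1) to 86% (R² = 0.4), a gain of 3 to 19 points. The 95% half-width for the mean difference falls from 1.90 to 1.83 (1 − 1.83/1.90 = 4%) or to 1.50 (1 − 1.50/1.90 = 21%). A further run with no link gives power of 54% v 55% (N = 30) and 75% v 75% (N = 50).

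**Step 4: what sample size alone allows.** For 30% v 60% with n per arm, power = Φ[(0.30 − 1.96√(2 × 0.45 × 0.55/n)) / √((0.21 + 0.24)/n)]. At n = 15 this is Φ[(0.300 − 0.356)/0.173] = 37%. At n = 25 it is Φ[(0.300 − 0.276)/0.134] = 57%.

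**The case against.** **The commitment is loose.** The aims are undefined, the sentence sits in a paragraph justifying the inclusion of children, and it speaks of evaluating age rather than adjusting for it. Section 8 also compares age and severity across arms, participants with non-participants, and completers with drop-outs. This stands as a reason to call it an inconsistency to reconcile. It does not remove it: those comparisons check balance and selection, and none uses age in an arm comparison of adverse events, adherence or satisfaction.

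**A reader might infer that these tests are conservative without qualification.** The documents do not support that. They show no link between age or GCS group and these outcomes, and set no significance level. With no link, chi-square at N = 50 rejects in 5.6–5.8% of trials across runs, and no power is lost by leaving the covariates out. Some of the Mann-Whitney shortfall at N = 30 belongs to the test itself (3.8–4.0% with no link).

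**A reader might infer that the whole primary aim is affected.** Table 1 stars four outcomes. Recruitment and retention are percentages there with no arm test, and recruitment precedes randomisation. The SDSC total score already has linear regression. Only adverse events are both starred and given an unadjusted arm test; adherence and satisfaction are not starred.

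**Adjustment is not free for yes/no outcomes.** This stands, as the second table shows, although part of the −5 at N = 50 reflects the different sizes of the two tests (5.6% v 4.6%).

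**The consequence for safety is limited.** Section 10 gives the DSMB cumulative serious adverse events by arm, so oversight does not hang on a significance test. This also stands.

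**Conclusion.** The inconsistency is on the page and needs no simulation: Section 5c and the minimisation point to analyses that use age and GCS group, while the adverse-event, adherence and satisfaction comparisons cannot.

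The statistical cost is conditional. For counts, Mann-Whitney size falls from about 4–4.6% with no link (3.8–4.8% across all runs) to about 2% with a strong link. Power is roughly 3–18 points below an adjusted rank analysis when both factors matter, and only 1–2 points below when age alone matters moderately. With no link, adjusting costs nothing. For yes/no outcomes the change is about −5 to +7 points, too small and too uncertain in sign to replace chi-square.

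These sizes rest on assumed age bands, GCS mix, event rates, harm effects and link strengths. The direction for counts agrees across both parameterisations. It would be wrong to conclude that this omission is what would hide a harm: at 15 to 25 per arm, the sample size does most of that.

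**What to change.** - **Total number of adverse events (Section 8 and Table 1).** Make the arm comparison a regression on ranks (rank-ANCOVA) with arm, age as a continuous variable and GCS group. Report the adjusted difference with its interval. Keep Mann-Whitney as a sensitivity result.
- **Likert satisfaction items.** Use the same method, with Mann-Whitney again as sensitivity.
- **Yes/no outcomes (any adverse event, adherence).** Keep chi-square. Add an age- and GCS-adjusted risk difference as a supportive estimate only, tested by re-randomisation under the Section 6 allocation or another small-sample method, not by a logistic score test.
- **Section 5c.** Reword the sentence to name the outcomes for which age is adjusted. Limiting it to effectiveness would remove the inconsistency, but would forgo the likely gain for counts.

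The cost is a few lines of text and slightly more analysis work. Both covariates are already collected for allocation. The change makes better use of the patients enrolled; it does not make the trial large enough to detect a moderate harm reliably.
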